7.5 Study Duration

- 1) The duration of the whole PMOS is estimated to be about 4 years.

- Study start: September 2012
-

- Recruiting phase: September 2012 - December 2014
 - Data completion: January 2018
 - End of study: The date on which statistical analysis dataset for Clinical Study Report becomes available
 - Data analysis and final report: April 2018 – October 2018
- 2) For each individual patient, the PMOS starts with the enrollment at the beginning of the treatment with adalimumab.
- Observation period
 - 104 weeks (or discontinuation of this study)
 - Discontinuation of this study
 - Patients within 52 weeks into this study: When adalimumab treatment is discontinued.
 - Patients after 52 weeks into this study: When any biologics other than adalimumab is administered.

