10.1. Overall

Name of data	Derivation and calculation methods
Age	The age on the start date of treatment should be calculated. However, if the birth date is unknown, the age described in the CRF should be used. Since it is obtained up to birth month and year in the CRF, the birth date should be the 1st of the month.
Number of survey institutions	It should be tabulated by institution code.
Number of patients surveyed	It should be tabulated by case (number).
Calculation of period	Period = the relevant date - the initial date +1
Definition of unit period	One week should be converted into seven days.
Date of initial Humira treatment	Of the start dates of treatment in Humira treatment status, the earliest date should be the date of initial Humira treatment.
Date of final Humira treatment	
Of the completion dates of treatment in Humira treatment status, the latest date should be the date of final Humira treatment.
 
However, the following measures should be taken according to the final record of each patient.
 
 • For patients whose the start date of treatment exceeds the planned completion date of each CRF and the completion date of treatment is described as “continuing,” the start date of treatment should be complemented to the complete date of treatment of the record. • For patients whose the start date of treatment is prior to the planned completion date of each CRF and the completion date of treatment is described as “continuing,” the completion date of treatment should be complemented to the complete date of treatment of each CRF. • If the start date of treatment with a biological product and the final record of the completion date of Humira treatment are the same date in the third CRF, the completion date of Humira treatment should be -1 day and the overlap of the treatment period should be deleted. 
*Planned completion date of each CRF First CRF: start date of Humira treatment + 167 days Second CRF: start date of Humira treatment + 363 days Third CRF: start date of Humira treatment + 727 days

Period to treatment completion (day)	It should be between the date of initial Humira treatment and the date of final Humira treatment.

Name of data	Derivation and calculation methods

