Treatment period (day) Completion date of treatment *Per record	
It should be between the start date of Humira treatment and the completion date of treatment per treatment record.
 
When the completion date of treatment in the information on the previous treatment within the same CRF and the start date of treatment in the information on the relevant treatment are the same date, the completion date of treatment in the information on the previous treatment should be - 1 day.
 
The records with the dose of 0 mg should be excluded from the analysis.

Dosing intervals (day) *Per record	Biweekly should be 14 days, once in three weeks should be 21 days, and once in four weeks should be 28 days, respectively.
Total number of doses	The total after calculating the number of doses per record by rounding up the first decimal place should be taken for treatment period (day)/dosing intervals (day).
Patients who discontinued Humira treatment	If the final fixed CRF is the first or second CRF, the patients should be handled as the patients with a description in the “treatment discontinuation” column in the final CRF. If the final fixed CRF is the third CRF, the patient should be handled as the patients with a description of the completion date of treatment in the final record of the “Humira treatment status” column in the final CRF.
Patients who are continuing Humira treatment	If the final fixed CRF is the first or second CRF, the patients should be handled as the patients without a description in the “treatment discontinuation” column in the final CRF. If the final fixed CRF is the third CRF, the patient should be handled as the patients with a description of “continuing” in the final record of the “Humira treatment status” column in the final CRF.
Date of treatment discontinuation	In patients who discontinued Humira treatment, the completion date of Humira treatment should be the date of discontinuation.
Low body weight	Patients with body weight of < 30 kg.
Date of survey discontinuation	It should be the date of survey discontinuation described in the third CRF. It should be the start date of treatment with other biological products, or the older date among the last follow-up date.
AE follow-up period	It should be between the date of initial Humira treatment and the date of initial Humira treatment + 755 days.

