Start date of MTX treatment *Per record	When there is more than one record of the same reason for use and same dose within the same patient and the treatment period is overlapped in these records, the information in the record in the latest CRF should be adopted and the start date of MTX treatment of the record should be used. The records with the dose of 0 mg should be excluded from the analysis.
Completion date of MTX treatment *Per record	When the completion date of treatment in the information on the previous treatment and the start date of treatment in the information on the relevant treatment are the same date within the same patient, the completion date of treatment in the information on the previous treatment should be - 1 day.
Treatment continuing group	Among the patients included in the efficacy analysis set (third CRF), patients who are continuously receiving Humira at week 104.

Name of data	Derivation and calculation methods
Treatment discontinued group	Among patients included in the efficacy analysis set (third CRF), patients whom the discontinuation date of Humira treatment and the relevant date at week 104 is ≥ 24 weeks apart of the patients continuing the survey who discontinued Humira treatment later than week 52. Or the patients whom the date of final follow-up (or the lower date of the start date of treatment with other biological product other than Humira) is ≥ 24 weeks apart from the date of Humira treatment discontinuation among the patients discontinued survey who discontinued Humira treatment later than week 52.
Survey discontinued group	Among the patients included in the efficacy analysis set (third CRF), the patients with the entry of the start date of treatment with other biological products other than Humira or the final follow-up date not applicable to the conditions for the treatment discontinued group.
Other groups	Among the patients included in the efficacy analysis set (third CRF), patients who are not applicable to the treatment continuing group, treatment discontinued group or survey discontinued group.

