Reason for discontinuation (third CRF)	Occurrence of AEs, symptom improved, inadequate response, patient refused treatment with Humira, others (pregnancy/desire for pregnancy, others), undescribed
Reason for survey discontinuation	Administration of biological products other than Humira, failed to visit hospital, others, undescribed

<Efficacy endpoints>

Data	Layer separation	
DAS28-4ESR	High Moderate Low Remission	> 5.1 > 3.2 and ≤ 5.1 ≥ 2.6 and ≤ 3.2 < 2.6
DAS28-4CRP	High Moderate Low Remission	> 5.1 > 3.2 and ≤ 5.1 ≥ 2.6 and ≤ 3.2 < 2.6
CDAI	High Moderate Low Remission	> 22.0 > 10.0 and ≤ 22.0 > 2.8 and ≤ 10.0 ≤ 2.8
SDAI	High Moderate Low Remission	> 26.0 > 11.0 and ≤ 26.0 > 3.3 and ≤ 11.0 ≤ 3.3
HAQ-DI	High Moderate Low Remission	> 1.5 > 1.0 and ≤ 1.5 > 0.5 and ≤ 1.0 ≥ 0 and ≤ 0.5
mTSS	Change (≤ 0) Change (≤ 0.5) Change (≤ 1.0)	Change ≤ 0 Change ≤ 0.5 Change ≤ 1.0
Bone erosion score	Change (≤ 0) Change (≤ 0.5) Change (≤ 1.0)	Change ≤ 0 Change ≤ 0.5 Change ≤ 1.0
Joint space narrowing score	Change (≤ 0) Change (≤ 0.5) Change (≤ 1.0)	Change ≤ 0 Change ≤ 0.5 Change ≤ 1.0

*Hereafter, “complete remission” refers to “Remission” in the above table.

12. Handling of data on test/evaluation time

For data entered at each timing of efficacy evaluation excluding mTSS, bone erosion score and joint space narrowing score, the acceptability of data by timing should be judged based on the acceptable range of the timing. The acceptable range of the timing is shown in the table below.

If there is more than one data within the acceptable range of the timing, the data on the closest date to the reference date should be adopted. If there is more than one data within the acceptable range of the timing with the equal number of days from the reference before and after the reference date respectively, the data before the reference date should be adopted.

When evaluating efficacy regarding administration of Humira, it should follow the following provision for the data included in the following acceptable range.

- The data up to the date of final Humira treatment + 28 days should be tabulated.

However, the date of final Humira treatment +28 days is later than the date of survey discontinuation, the data up to the date of survey discontinuation should be tabulated.

This date is called [final evaluation date] in the following.

Timing and period category	Handling of data

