Note: 10.1 “Humira treatment period” should be used as the total treatment period including washout as the period to treatment completion.
<Detailed note>

- 1) When the patient was continuing the treatment at week 104, the patient was tabulated as “continuing treatment.”

“Table 3.2.1 Disposition of reasons for discontinuation of Humira treatment (first and second CRFs)”

Analysis object: Patients included in the safety analysis set

Purpose of analysis: To indicate the number and percentage of patients for the disposition of the reasons for discontinuation of Humira treatment.
The reasons for discontinuation should follow “11. Data-layer separation.”

Note: The denominator of the percentage of the number of discontinued patients should be the number of patients included in the safety analysis set, and the denominator of the percentage of the number of patients by reason for discontinuation should be the number of overall discontinued patients.
<Detailed note>

When a patient is applicable to more than one items, each of them was counted.

“Table 3.2.2 Disposition of reasons for survey discontinuation (third CRF)”

Analysis object: Patients included in the safety analysis set

Purpose of analysis: To indicate the number and percentage of patients for the disposition of the reasons for discontinuation of the survey discontinued patients in the third CRF. The number and percentage of patients should also be indicated for the

disposition of the reasons for discontinuation of the patient who discontinued treatment in the third CRF. The reasons for discontinuation should follow “11. Data-layer separation.”

Note: The denominator of the percentage of the number of discontinued patients should be the number of patients with fixed CRFs at week 104 among the patients included in the safety analysis set, and the denominator of the percentage of the number of patients by reason for discontinuation should be the number of overall discontinued patients by reason for survey discontinuation and treatment discontinuation.

The patients applicable to survey discontinuation should not be included in the number of treatment discontinued patients. The reasons for treatment discontinuation should be the change in dose/number of doses or reason for discontinuation of the final record in the “Humira treatment status” in the third CRF.

<Detailed note>

When a patient is applicable to more than one items, each of them was counted.

“Table 5.1 Frequency of ADRs by seriousness”

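### End of treatment and third-CRF status come only from the last Humira record, so many patients who stop adalimumab after week 52 and restart it leave the discontinued group, and drug-free values can be tabulated as Humira data

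*SAP*

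**What the plan says.** **Observation after stopping.** Under Protocol 7.5, a patient leaves the study when adalimumab stops within the first 52 weeks. Later, observation ends only as follows: "Patients after 52 weeks into this study: When any biologics other than adalimumab is administered". Stopping and restarting adalimumab on study is therefore possible after week 52.

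**End of treatment.** SAP 10.1: "Of the completion dates of treatment in Humira treatment status, the latest date should be the date of final Humira treatment". A patient recorded as ongoing in the third CRF is given an end date of day +727, counted from the first dose.

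**Status.** When the third CRF is the last one fixed, SAP 10.1 takes patients as continuing if they are "with a description of “continuing” in the final record of the “Humira treatment status” column in the final CRF", and as discontinued if they are "with a description of the completion date of treatment in the final record of the “Humira treatment status” column in the final CRF". Humira records with a dose of 0 mg are dropped. A discontinuation date is defined only for patients classed as discontinued.

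**Third-CRF groups (SAP 10.1).** The treatment continuing group is "patients who are continuously receiving Humira at week 104". The treatment discontinued group needs at least 24 weeks between discontinuation and week 104. For patients who left the survey, the 24 weeks run to the last follow-up or the start of another biologic. The remaining patients form the survey discontinued group or Other groups.

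**Data cut-off (SAP section 12).** For the clinical scores: "The data up to the date of final Humira treatment + 28 days should be tabulated". An earlier survey discontinuation date takes precedence. For X-ray scores the allowance is 56 days.

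**Gaps.** The only explicit mention is the note to Table 3.1 in SAP 13.2, where the period to treatment completion is the "total treatment period including washout". Neither document has a rule for restarting adalimumab.

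**The concern.** Tables 6.1.2 and 6.9.2 are the only efficacy summaries that set patients who continued adalimumab beside patients who stopped it. Restart is plausibly linked to relapse. If restarting moves a patient out of the discontinued row, membership of that row depends partly on the outcome it reports.

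A second problem concerns the tables by visit. The SAP limits efficacy data to 28 days after the final stop but sets no such limit after an earlier stop. A score taken months into a drug-free gap is excluded if the patient never restarts and included if the patient does.

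**Working it through.** **1. Figures in the plan.** The plan gives none for restarts. Its one checkable design figure, the week-52 sample size, reproduces: a one-sample test of 55% against 42.7%, two-sided 5%, 90% power, gives 170.7, rounded up to 171; 171/0.5 = 342. It does not enter this point.

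**2. Inputs, in days from first dose.** Week 104 = 728. The 24-week rule = 168 days, so a patient followed to week 104 must have a last stop by 728 − 168 = 560 to be in the discontinued group. Entry to the third-CRF efficacy set (SAP section 8) needs a final Humira date later than 364 + 28 = 392. The week-76 window is 504 to 560 and the week-104 window 700 to 756. The clinical cut-off is the final Humira date + 28.

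**3. The rules applied to example histories.** The week-76 value is taken at day 532.

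| History | Final Humira date | Third-CRF group | Week-76 value |
|---|---|---|---|
| A: stop 420, no restart | 420 | Discontinued (728 − 420 = 308 ≥ 168) | Excluded (532 > 448) |
| B: stop 420, restart 590, ongoing | 727 | Continuing, or Other groups | Tabulated (532 ≤ 755), 532 − 420 = 112 days off drug |
| C: stop 420, restart 470, last stop 540 | 540 | Discontinued (728 − 540 = 188 ≥ 168) | Tabulated, on drug |
| D: stop 420, restart 590, last stop 650 | 650 | Neither continuing nor discontinued (728 − 650 = 78 < 168) | Tabulated (532 ≤ 678), 112 days off drug |
| E: stop 380, no restart | 380 | Outside the third-CRF set (380 < 392) | Excluded (532 > 408) |
| F: stop 380, restart 560, ongoing | 727 | Continuing, or Other groups | Tabulated (532 ≤ 755), 532 − 380 = 152 days off drug |
| G: stop 400, restart 720, ongoing | 727 | Continuing, or Other groups | Tabulated (532 ≤ 755), 532 − 400 = 132 days off drug |

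A and B have the same first stop and the same drug-free week-76 visit. Only the later restart separates them. In B, F and G the group depends on whether continuous receipt means treated at week 104 or treated without a gap; on neither reading is the patient in the discontinued group. C stays in that group but is timed from day 540 and not from 420. In G, a week-104-window value at day 710 is also tabulated, 710 − 400 = 310 days off drug. That needs a restart in or after the window; B is back on drug by then.

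**4. Possible effect on the discontinued row.** Let p be the true drug-free remission rate among all who stopped, and f the share of relapsers who restart and leave the group. The patients left in the row are p + (1 − p)(1 − f) = 1 − (1 − p)f, so the row shows p / [1 − (1 − p)f]. Both p and f are assumptions.

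| p | f = 25% | f = 50% | f = 75% |
|---|---|---|---|
| 40% | 47.1% | 57.1% | 72.7% |
| 50% | 57.1% | 66.7% | 80.0% |
| 60% | 66.7% | 75.0% | 85.7% |

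For example, 0.50 / (1 − 0.50 × 0.50) = 66.7%. With f = 0 the row is unbiased.

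**The case against.** The strongest case against is that this is a minor gap in descriptive tables. No protocol objective concerns outcomes after stopping adalimumab, no restart is reported anywhere, and counting washout in the treatment period is a stated convention. Table 1.2 (third CRF) counts all four groups, and List 8.2 gives patient-level data. These points limit the consequence. They do not remove the inconsistency with the SAP's own 28-day limit, and neither a disposition count nor a listing summarises outcome among all who stopped.

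Several stronger readings are tempting, and the documents do not support them:

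- *Every restarter leaves the discontinued group.* History C shows otherwise: a last stop by day 560 keeps the patient in.
- *The discontinued row is selected for not relapsing.* Relapsers who stay off drug remain in it, as do patients who start another biologic at least 24 weeks after stopping. Patients also stop for adverse events or pregnancy, so a restart need not mean relapse.
- *The continuing row absorbs the failures.* This holds only if continuous receipt tolerates a gap; otherwise these patients fall into Other groups.
- *The visit tables are affected throughout.* The effect is mainly at week 76, and only where a visit falls inside the gap.
- *Adverse events in the gap are generally misfiled.* Table 5.3.1 splits events into during and after treatment only for patients who discontinued, so this mainly concerns those who restart and stop again.

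The handling criteria for patients are not among the documents and might address interruptions. SAP section 8 cites them only for exclusion from analysis sets.

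**Conclusion.** The point holds, within limits. As written, the rules take out of the treatment discontinued group any patient who stops after week 52, restarts, and is either still treated at week 104 or, if followed to week 104, has a last stop after day 560. They also let drug-free values from the gap into Tables 6.1 to 6.7 beyond the 28 days that the SAP allows after a final stop. Where restart follows relapse, the discontinued rows of Tables 6.1.2 and 6.9.2 can look better than the result for all who stopped.

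The size is unknown because neither document gives a restart or relapse rate. In the illustrated range the row exceeds the true figure by about 7 to 33 percentage points (66.7 − 60 = 6.7; 72.7 − 40 = 32.7), assuming that only relapsers restart and that every restarter leaves the group. With few restarters the difference would be small. The week-52 primary endpoint and the sample size are unaffected.

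**What to change.** 1. In SAP section 12, apply the existing allowance (28 days; 56 days for X-ray scores) after the end of each Humira treatment record, not only the last. Values in a longer gap then stay out of the week-76 and week-104 Humira columns. Records that follow one another without a gap are unaffected.
2. Identify the first stop after week 52 from the treatment records, using 0 mg records to locate gaps, and state the minimum gap that counts as a stop. In Tables 6.1.2 and 6.9.2 add a row for patients who stopped and restarted adalimumab and a total for all who stopped. Keep the 24-week rule for the existing discontinued row. State how first stops up to day 392 are handled, because such patients now enter the third-CRF set only if they restart (histories E and F).
3. In the new row use only values measured inside the gap and beyond the 28- or 56-day allowance. Where there is none, count the patient as restarted without a drug-free value, and do not carry forward an on-drug value. Visits in this period are scheduled only at weeks 76 and 104, so some patients will have no usable value.
4. Say whether continuous receipt at week 104 permits an earlier gap.

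The cost is SAP wording and some programming on records already collected, with no change to clinical conduct. The downsides are slightly fewer values in the Humira columns and a possibly less favourable stopped-treatment summary. If nobody restarted, the new row shows zero and settles the question.

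### SAP 10.1 extends a last Humira record marked continuing to the planned CRF end, with no cap at survey discontinuation, so patients lost after week 52 are credited with unobserved treatment time

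*SAP*

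**What the plan says.** SAP 10.1 gives two rules for a last treatment record marked as continuing.

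- If the record starts before the planned completion date of the CRF, "the completion date of treatment should be complemented to the complete date of treatment of each CRF". The footnote lists the planned dates, ending with "Third CRF: start date of Humira treatment + 727 days".
- If the record starts after the planned completion date, "the start date of treatment should be complemented to the complete date of treatment of the record".

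The only adjustment linked to another biologic applies when its start and the recorded end of Humira fall on the same day in the third CRF: "the completion date of Humira treatment should be -1 day and the overlap of the treatment period should be deleted".

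Period to treatment completion is built directly on this date: "It should be between the date of initial Humira treatment and the date of final Humira treatment". Total doses use the completion date of each record.

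SAP 10.1 also defines the date of survey discontinuation: "It should be the date of survey discontinuation described in the third CRF", based on the start of another biologic or the last follow-up. For the third CRF, SAP 11 lists the survey discontinuation reasons as "Administration of biological products other than Humira, failed to visit hospital, others, undescribed". The third-CRF reasons for stopping Humira do not include missed visits. In the first and second CRFs, missed visits are a reason for stopping treatment.

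**The concern.** Under Protocol 7.5, after week 52 a patient leaves the study when another biologic is given; stopping adalimumab alone does not end observation. In the third CRF, loss to follow-up is therefore recorded as leaving the survey, and the last Humira record can properly still read continuing. The rule in SAP 10.1 then fills the gap between the last contact and day 728 with treatment that nobody observed.

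The error runs in one direction: it lengthens treatment and flatters persistence. It reaches three outputs:

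- **Period to treatment completion**, summarised in Table 3.1.
- **Total number of doses.**
- **The continuation curves.** Table 5.8.1 states no censoring rule. Table 5.8.2 names only patients still on Humira after day 728 as censored. A lost patient carried to day 728 stays in the risk set throughout.

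**Working it through.** **Step 1. Reproduce the plan's day count.** SAP 10.1 gives "Period = the relevant date - the initial date +1". The planned CRF ends are start + 167, + 363 and + 727 days.

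- First CRF: 167 + 1 = 168 days = 24 weeks
- Second CRF: 363 + 1 = 364 days = 52 weeks
- Third CRF: 727 + 1 = 728 days = 104 weeks

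The figures agree with the visit schedule and support reading the first rule as the planned completion date.

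**Step 2. Look for a cap.** Neither rule for a continuing record refers to survey discontinuation. The second rule cannot apply to someone who left before the planned end. The biologic adjustment removes one day and needs a recorded end of Humira. SAP 12 does stop data at survey discontinuation, but only for efficacy and X-ray data.

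**Step 3. One patient.** Assume one Humira record at 14-day intervals, marked continuing in the third CRF. Excess = 728 − (last-seen offset + 1). Doses = days/14, rounded up.

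| Last seen | Observed days | Credited days | Excess days | Doses, observed vs credited |
|---|---|---|---|---|
| Week 53 (start + 371) | 372 | 728 | 356 | 27 vs 52 |
| Week 76 (start + 532) | 533 | 728 | 195 | 39 vs 52 |
| Week 88 (start + 616) | 617 | 728 | 111 | 45 vs 52 |

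**Step 4. The continuation curve.** The documents give no loss rate after week 52, so these inputs are assumptions: among patients on Humira at week 52, a true stopping risk D of 10-30% and a loss risk L of 5-20% by week 104, constant independent hazards, every lost patient marked continuing, and patients carried to day 728 treated as censored there.

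Let a = −ln(1 − D), b = −ln(1 − L), s = a + b, with 364 days as the time unit.

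- Censoring at loss: continuation = 1 − D
- SAP rule: continuation = 1 − (a/s) × [1 − (1 − D)(1 − L)]

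For D = 20% and L = 10%: a = 0.2231, b = 0.1054, a/s = 0.679, and 1 − 0.80 × 0.90 = 0.28. Continuation = 1 − 0.679 × 0.28 = 0.810, against 0.800 with censoring: 1.0 point too high.

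At the extremes, D = 10% with L = 5% gives an excess of 0.25 points, and D = 30% with L = 20% gives 2.93. A simulation of 40,000 patients per setting gave 0.26 and 2.90.

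**Step 5. Treatment time after week 52.**

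- Mean time with censoring at loss: c = [1 − (1 − D)(1 − L)]/s
- Mean time under the SAP rule: i = 1 − (a/s)(1 − c)

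For D = 20% and L = 10%: c = 0.28/0.3285 = 0.852 and i = 1 − 0.679 × 0.148 = 0.900. The ratio is 1.056, an inflation of about 5.6%. Over the whole grid it is about 3-12%. Measured over total treatment time from the start of Humira, it is about 1-5%.

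**The case against.** The strongest reply is that the premise depends on how sites complete the third CRF, and its instructions are not in the documents. If a site enters a last known treatment date when a patient is lost, nothing is filled in. A patient whose last CRF is the second is credited only to day 364. The primary endpoint at week 52 is untouched, and Tables 5.8.1 and 5.8.2 are descriptive and prepared only for the literature analysis. All of this stands and limits the importance of the point. It does not supply the missing cap.

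A reader might also infer more than the text supports.

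- **Each lost patient as a retention error.** If 10-20 of 350 patients were lost (an assumption), retention might seem too high by 10/350 = 2.9 to 20/350 = 5.7 points. That counts every lost patient as having stopped. Censoring makes no such assumption, and the comparison in step 4 gives a smaller figure.
- **Diluted safety rates.** Tables 5.3.1 and 5.3.2 report numbers of events, and unobserved time adds none. Table 5.2.4 divides by a total follow-up period that the SAP does not define, so an effect there cannot be established.
- **The continuing class in Table 3.1.** The filled-in date gives exactly 728 days, so it does not meet the 729-day limb. Membership comes from the CRF entry. The definitions conflict: the SAP 11 table accepts at least 729 days or a continuing entry, its footnote requires more than 728 days and a continuing entry, and the Table 3.1 note refers to patients continuing at week 104.
- **Contaminated efficacy groups.** SAP 12 cuts efficacy data at survey discontinuation. SAP 10.1 limits the treatment continuing group to patients receiving Humira at week 104 and has a separate survey discontinued group.

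**Conclusion.** The point holds for treatment duration, dose counts and the continuation curves. As written, SAP 10.1 counts unobserved time as treatment for any patient who leaves the survey after week 52 with a last third-CRF record marked continuing. The excess per affected patient runs from 1 to about 363 days.

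The effect on the cohort rests on the assumed rates and hazards in step 4. Within those ranges, continuation from week 52 to week 104 is overstated by about 0.3-2.9 percentage points compared with censoring. Fewer continuing entries among lost patients would make it smaller. This is a modest bias in secondary descriptive results, worth correcting because its direction is known and the date needed is already collected. The documents do not support extending it to the effectiveness results or to safety rates.

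**What to change.** 1. In SAP 10.1, for a last record marked continuing, set the date of final Humira treatment to the earlier of the planned CRF completion date and the date of survey discontinuation (start of another biologic or last follow-up).
2. State in Tables 5.8.1 and 5.8.2 that patients lost to follow-up are censored at that date.
3. Reconcile the definitions of continuing treatment in SAP 11 and the Table 3.1 note, so that patients who left the survey before week 104 are not placed in that class.

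The cost is one sentence in SAP 10.1, a line of derivation code and two clarifying notes. No new data are needed. Reported retention becomes slightly less favourable.
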